15.1.2.5 Section 6.4.1 Withdrawal criteria

This section was changed as a result of Modification 3.

Old text:

Patients **must be withdrawn from the study** if any of the following occurs:

- [...]
- ~~If any investigational drug other than the study drug is used during the study period.~~

New text:

Patients **may be withdrawn from the study** if any of the following occurs:

- [...]
- If any investigational drug other than the study drug is used during the study period.

15.1.2.6 Section 7.5 Blinding

This section was changed as a result of Modifications 4 and 9.

Old text:

Table 7–3: Assignment of tablets to dose groups

Treatment arm/ Formulation	5 mg	10 mg	20 mg	30 mg	40 mg	Placebo
5 mg	1	2	0	0	0	0
10 mg	0	0	2	1	0	0
20 mg	0	0	0	1	2	0
Placebo	1	0	0	0	0	2
Total tablets/day	2	2	2	2	2	2

New text:

Table 7–3: Assignment of tablets to dose groups

Treatment arm/ Formulation	5 mg	10 mg	20 mg	30 mg	40 mg	Placebo
5 mg	1	0	0	0	0	0
10 mg	0	1	0	1	0	0
20 mg	0	0	1	1	2	0
Placebo	1	1	1	0	0	2
Total tablets/day	2	2	2	2	2	2

Added text:

The following parties will be unblinded: sponsor’s IxRS and Medication Manager, Clinical Supply Manager and Clinical Pharmacometrics analyst (who will be provided with a randomization list for selected bioanalyses of the active metabolite BAY 84-3174 in plasma), the drug supply’s Project Manager, and the DMC.

For all other sponsor’s study personnel, the Steering Committee and the Clinical Events Committee (CEC) the blinding will be strictly kept.

15.1.2.7 Section 8.1.1 Prohibited concomitant medication

This section was changed as a result of Modifications 2 and 5.

The same changes were made to the list of excluded medications as described in Section 15.1.2.4. In addition, the following text was added:

A list of prohibited medications will be provided to the investigators.

If a prohibited concomitant medication (e.g. moderate / strong CYP3A4 inhibitor) is used during the study conduct, the study drug should be interrupted immediately and restarted as soon as possible, when the prohibited medication has been stopped. Prior to re-starting the study drug, a washout period of at least two days after discontinuation of the prohibited medication should be adhered to.

15.1.2.8 Section 8.1.2 Permitted therapy

This section was changed as a result of Modification 6.

Added text:

Neladenoson bialanate is a weak Breast Cancer Resistance Protein (BCRP) inhibitor. The risk of clinically relevant drug–drug interactions at doses up to 40 mg BAY 1067197 due to inhibition of BCRP is regarded as low, but cannot be excluded (BCRP substrates are atorvastatin, simvastatin, rosuvastatin, fluvastatin, methotrexate, etc.; a list of BCRP substrates will be made available to the investigators).

If neladenoson bialanate is given concomitantly with other drugs that may increase the exposure of BCRP substrates, the respective drug labels should be consulted.

15.1.2.9 Section 9.1 Tabular schedule of evaluations

This section was changed as a result of Modification 9.

Old text (“dots” were replaced by “pre-dose”):

Week Day and allowed deviations	-1 -7	W0 0+2
Blood sample for safety		•
Blood sample for biomarkers		•
Urine sample for biomarkers		•

New text:

Week Day and allowed deviations	-1 -7	W0 0+2
Blood sample for safety		pre-dose
Blood sample for biomarkers		pre-dose
Urine sample for biomarkers		pre-dose

Old text:

g [...] If a patient does not take the study drug before the visit, he / she can take it at the start of the visit, in which case PK sampling will occur ~~2 and 4 hours after the study drug intake~~.

New text:

g [...] If a patient does not take the study drug before the visit, he / she can take it at the start of the visit, in which case PK sampling will occur as described above.

15.1.2.10 Section 9.2 Visit description

This section was changed as a result of Modification 9.

The following sentence was added to Visit 4 (Week 4) and Visit 5 (Week 8):

Ideally, the study personnel should contact the subject prior to Visit 4/Visit 5 to remind them not to take the study drug as usual in the morning at home.

15.1.2.11 Section 9.4.2 Biomarker investigations

This section was changed as a result of Modification 9.

Deleted text:

Mandatory (sampled at all time points):

- High sensitivity troponin T (hs-TNT) (baseline disease status ~~& safety~~)
- Cystatin C (baseline disease status, ~~safety & efficacy~~)

15.1.2.12 Section 9.6.3.5 AVIVO monitoring

This section was changed as a result of Modification 9.

Old text:

Apart from safety assessments, also the patient's everyday physical activity (~~frequency,~~ duration, intensity) will be tracked.

New text:

Apart from safety assessments, also the patient's everyday physical activity (e.g. duration, intensity) will be tracked.

15.1.2.13 Section 10.3.1.3 Other exploratory variables

This section was changed as a result of Modification 9.

Old text:

- Activity (~~frequency,~~ duration, intensity) reported values and absolute change from baseline at 20 weeks

New text:

- Activity (duration, intensity) reported values and absolute change from baseline at 20 weeks

15.1.2.14 Section 10.3.2.2 Analysis of the primary efficacy variables

This section was changed as a result of Modification 8.

Old text:

Table 10–1: Dose-response shapes used in the candidate set

Model	Response as function of dose d	
	LVEF	NT-proBNP
Linear	$2 + 0.075d$	$-0.105 - 0.005425d$
Sigmoidal E_{\max} 1	$2 + 3.007689d^4 / (9^4 + d^4)$	$-0.105 - 0.21756d^4 / (9^4 + d^4)$
Sigmoidal E_{\max} 2	$2 + 3.375d^3 / (20^3 + d^3)$	$-0.105 - 0.24413d^3 / (20^3 + d^3)$
E_{\max}	$2 + 3.09375d / (1.25 + d)$	$-0.105 - 0.22378d / (1.25 + d)$
Quadratic	$2 + 0.2d - 0.00333d^2$	$-0.105 - 0.01447d + 0.00241d^2$

New text:

Table 10–1: Dose-response shapes used in the candidate set

Model	Response as function of dose d	
	LVEF	NT-proBNP
Linear	$2 + 0.075d$	$-0.105 - 0.0063d$
Sigmoidal E_{\max} 1	$2 + 3.007689d^4 / (9^4 + d^4)$	$-0.105 - 0.2526d^4 / (9^4 + d^4)$
Sigmoidal E_{\max} 2	$2 + 3.375d^3 / (20^3 + d^3)$	$-0.105 - 0.2835d^3 / (20^3 + d^3)$
E_{\max}	$2 + 3.09375d / (1.25 + d)$	$-0.105 - 0.2599d / (1.25 + d)$
Quadratic	$2 + 0.2d - 0.00333d^2$	$-0.105 - 0.0168d + 0.00028d^2$

15.1.2.15 Section 11.1 Data recording

This section was changed as a result of Modification 9.

Added text:

Patient data necessary for analysis and reporting will be entered / transmitted into a validated database or data system (e.g. TOSCA; SAS).

15.1.2.16 Section 13.1 Investigator(s) and other study personnel

This section was changed as a result of Modification 7.

Old text:

Clinical Events Committee

Blinded adjudication of all hospitalizations and deaths will be performed by a central CEC as described in the CEC ~~manual~~. Data entry procedures and documentation necessary for case adjudication will also be described in the CEC ~~manual~~.

New text:

Clinical Events Committee

Blinded adjudication of all hospitalizations, urgent visits for HF and deaths will be performed by a central CEC as described in the CEC charter. Data entry procedures and documentation necessary for case adjudication will also be described in the CEC charter.

16. Appendices

16.1 Calculating glomerular filtration rate

In accordance with established nephrology practice and guidelines, renal function at baseline and throughout the study will be assessed by means of the estimated glomerular filtration rate (eGFR), calculated using the Modification of Diet in Renal Disease (MDRD) study abbreviated formula.

Isotope dilution mass spectroscopy (IDMS)-traceable MDRD Study Equation:

Conventional units (serum creatinine level is measured in mg/dL)

$$\text{GFR (mL/min/1.73 m}^2\text{)} = 175 \times (\text{serum creatinine})^{-1.154} \times (\text{Age})^{-0.203} \times (0.742 \text{ if female}) \times (1.212 \text{ if African American})$$

GFR can be estimated using the calculator provided in the following link:

http://www.kidney.org/professionals/kdoqi/gfr_calculator

For further information on assessing renal function using GFR estimates, see reference (48).

16.2 Calculating the Child-Pugh score

The severity of liver disease (Table 16–1) will determine the Child-Pugh score (Table 16–2).

Table 16–1: Grading of severity of liver disease

Factor	+1	+2	+3
Bilirubin (mg/dL)	< 2	2 – 3	> 3
Albumin (g/dL)	> 3.5	2.8 – 3.5	< 2.8
International Normalized Ratio	< 1.7	1.7 – 2.3	> 2.3
Ascites	None	Mild	Moderate / Severe
Encephalopathy	None	Grade I - II	Grade III – IV

Source: adapted from (49)

Table 16–2: Classification using the added score from Table 16–1

Child-Pugh Class	A	B	C
Points	5 – 6	7 – 9	10 – 15

Source: adapted from (49)

eGFR	estimated glomerular filtration rate
EQ-5D-5L	EuroQol Group 5-dimensional, 5-level questionnaire
EU	European Union
EWDT	E-wave deceleration time
FAS	full analysis set
GFR	glomerular filtration rate
GGT	gamma glutamyl transpeptidase
HDL	high-density lipoprotein
HF	heart failure
HFpEF	heart failure with preserved ejection fraction
HFrfEF	heart failure with reduced ejection fraction
HR	heart rate
hs-TNT	high sensitivity troponin T
i.e.	that is (id est)
ICF	informed consent form

Statistical Analysis Plan

Protocol No.: **BAY 1067197/15128**

Page: 5 of 39:

ICH	International Conference on Harmonization
INR	international normalized ratio
ITT	intent-to-treat
IVSD	interventricular septum diameter
KCCQ	Kansas City cardiomyopathy questionnaire
LA	left atrial
LAV	LA volume
LAVI	LA volume index
LDH	lactate dehydrogenase
LDL	low-density lipoprotein
LV	left ventricular
LVEDV	LV end-diastolic volume
LVEDVI	LVEDV index
LVEF	left ventricular ejection fraction
LVESV	left ventricular end-systolic volume
LVESVI	LVESV index
MAP	mean arterial pressure
MCH	mean corpuscular hemoglobin
MCHC	MCH concentration
MCP	multiple comparison procedures
MCV	mean corpuscular volume
MedDRA	Medical Dictionary for Regulatory Activities
mL	milliliter
MRA	mineralocorticoid receptor antagonist
NGAL	neutrophil gelatinase-associated lipocalin
NONMEM	non-linear mixed effect modeling
NT-proBNP	N-terminal pro-hormone b-type natriuretic peptide
NYHA	New York Heart Association
PASP	pulmonary artery systolic pressure
PDV	premature discontinuation visit
Pes	end-systolic pressure
pg	picogram
PK	pharmacokinetic
PKS	PK analysis set
PP	pulse pressure
PPS	per-protocol set
PTT	partial thromboplastin time
PWT	posterior wall thickness
RV	right ventricular
SAC	systemic arterial compliance

Statistical Analysis Plan

SAE(s)	serious adverse event(s)
SAF	safety analysis set
SAP	statistical analysis plan
SBP	systolic blood pressure
SV	stroke volume
SVI	SV index
TAPSE	tricuspid annular plane systolic excursion
TD	tissue Doppler
TPR	total peripheral resistance
UACR	urine albumin-to-creatinine ratio
US	United States (of America)

1. Introduction

Chronic heart failure (CHF) is a major public health problem characterized by significant mortality, frequent hospitalizations, and poor quality of life, with an overall prevalence that is increasing throughout the world. HF carries a prognosis comparable to many forms of cancer with a 5-year survival rate of approximately 50% (1), which exceeds that of many cancers (2). Frequent hospitalizations, along with other direct and indirect costs, also place an enormous financial burden on healthcare systems; more is spent annually in the US for the treatment of HF by Medicare than on any other Medicare-covered condition (3). Upon hospitalization for HFrEF mortality and re-hospitalization for HF remain high despite treatment with stable chronic HFrEF neurohumoral blockers, indicating that this does not fully explore the complexity of HF pathophysiology. Additionally, the repeated stepwise addition of hemodynamically active medications raises tolerability and safety concerns (e.g. hypotension and bradycardia) (4).

Therefore, addressing the failing heart directly and getting viable but not functional myocardium back to work might be a new option for the development of the next generation of hemodynamically silent HF drugs. In this context, neladenoson bialanate holds promise as a potentially hemodynamically neutral therapy for HF that could simultaneously improve cardiomyocyte energetics, calcium homeostasis, cardiac structure and function, and long-term clinical outcomes when added to background therapies.

Neladenoson bialanate (BAY 1067197, which is the free base of the hydrochloride BAY 86-8901) is the pro-drug of the pharmacologically active compound BAY 84-3174, a highly potent and selective non-adenosine like partial adenosine A1 receptor agonist suitable for once daily oral use.

The main limitations of using full A1R agonists in cardiovascular indications such as HF are undesired cardiac effects, such as bradycardia and higher degree AV block as well as negative cardiac inotropy and dromotropy. In contrast, preclinical data show that the partial adenosine A1R agonist neladenoson bialanate can be used to modulate and trigger primarily favorable pharmacological responses for HF therapy and avoid undesired effects such as AV conduction abnormalities and higher degree AV Block. Nevertheless, based on the mode of action, there are theoretical concerns particularly with regard to undesired effects, such as bradycardia and higher degree AV block for an A1R agonist, which might be aggravated by concomitant use of standard heart failure therapy.

The purpose of this clinical trial is to assess the safety, tolerability and the pharmacokinetic and pharmacodynamic response of 20 weeks' treatment with neladenoson bialanate compared to placebo in patients with chronic HFrEF on standard therapy for HF and to find the optimal dose for a further Phase III trial.

This statistical analysis plan (SAP) is based on the Global Integrated Clinical Study Protocol BAY 106-7197/15128 version 2.0, dated 17 FEB 2017.

2. Study Objectives

The objective of the study is to find the optimal dose of neladenoson bialanate for the Phase III trial by detecting and characterizing a significant dose-response relationship in the two

[figure not shown]
primary efficacy endpoints, absolute change from baseline in LVEF and log-transformed NT-proBNP at 20 weeks, in patients with chronic heart failure with reduced ejection fraction (HFrEF), and by characterizing the safety, tolerability and pharmacodynamic effects of the compound when given in addition to standard therapy for HFrEF.

An exploratory objective is to further assess pharmacokinetic parameters and blood and urine biomarkers.

3. Study Design

Study 15128 is a randomized, double-blind, placebo-controlled, parallel group, multicenter, Phase II study. Figure 3–1 displays the overall study design.

Figure 3–1: Study design overview

Abbreviations: CV = cardiovascular; ICF = informed consent form; W = week

Approximately 384 patients from approximately 90 study centers worldwide will be randomized to one of the active treatment dose arms or placebo, in addition to standard of care heart failure therapy (for details see Section 7).

The study will comprise a 1-week run-in period, 20-week treatment period, and a 6-week follow-up period (27 weeks total).

Patients will have site visits at weeks -1, 0 (baseline), 4, 8, 12, 20 (end-of-treatment visit) and 24 (safety follow-up visit). In addition, 2 phone calls at weeks 2 and 26 will be made to assess patients' safety, and one additional phone call - to remind the patients of AVIVO self-application at Week 19.

LVEF will be measured by echocardiography at baseline and end of treatment, NT-proBNP will be measured at baseline, Week 4 and end of treatment. Safety will be monitored throughout the study. PK samples will be taken from all patients at dedicated time points.

Additional biomarkers reflecting the pharmacodynamic activity of the drug will be examined, as well as candidate biomarkers that may predict drug response.

For detailed visit descriptions and rules for patients who discontinue study treatment earlier, please see protocol Sections 9.1 and 9.2.

The anticipated duration of the study as a whole is approximately 19 months: this includes an anticipated recruitment period of 13 months followed by a run-in period of 1 week, a treatment period of 20 weeks and a follow-up period of 6 weeks after enrollment of the last patient into the trial.

A parallel group design was chosen to compare five different once-daily dose regimens and one placebo arm to find the best dose for Phase III. Placebo control is used to control for observer and subject bias, and randomization - to control for assignment bias. Based on Phase I data in healthy volunteers and Phase II data on heart failure patients, a sequential dose escalation design was not deemed necessary for neladenoson bialanate since the safety profile of the compound could be verified in dose ranges up to 40 mg. Safety of the subjects in this parallel study design will be closely monitored by an Data Monitoring Committee (DMC).

The end of the study as a whole will be reached as soon as the last visit of the last patient has occurred in all centers in all participating countries (EU and non-EU).

4. General Statistical Considerations

4.1 General Principles

The statistical evaluation will be performed by using the software package SAS version 9.2 or higher (SAS Institute Inc., Cary, NC, USA). Unless otherwise noted, data will be analyzed by descriptive statistical methods: The number of data available and missing data, mean, standard deviation, minimum, quartiles, median, and maximum will be calculated for metric data. Frequency tables will be generated for categorical data.

Definition of efficacy and safety endpoints, analysis strategies, structure of analysis datasets and layout of analysis data displays are following Bayer AG standards: Neladenoson bialanate Project Standards, the Therapeutic Area Cardiovascular Standards (TAS) and the Global Medical Standards (GMS), respectively. The given ordering reflects the priority of the different standards, i.e. specifications of the latter ones have to be followed only if not specified in standards mentioned before. Study-specific specifications may be included in addition to the Project Standards, if needed.

4.2 Handling of Dropouts

A “dropout” is defined as a subject who has been randomized and discontinues study participation prematurely for any reason. Subjects withdrawn from study treatment will not be replaced. Refer to Section 6.4 in the Clinical Study Protocol for withdrawal of subjects from study.

See following chapters for more details on deriving efficacy endpoints in case of missing data.

4.3 Handling of Missing Data

All missing or partial data will be presented in the patient data listing as they are recorded in the eCRF.

A number of descriptive analyses will be performed to better understand missing data patterns. The frequency, proportion and the reasons for premature discontinuation of both the study and study treatment will be reported. Kaplan-Meier plots for “time to end of study treatment (calculated as days from first dose to the earliest date of stop medication, including premature stop of study medication and death, for the calculation all the subjects will be considered to have an event-stop of study medication)” and “time to end of study”(calculated from randomization to the earliest date of visit 9, death, and the last visit if subject drops off from study prematurely, for the calculation all the subjects will be considered to have an event-stop of study) will be provided, by treatment group and overall.

The number of patients who prematurely discontinue study participation or intake of study medication will be summarized with respect to the key subgroups, see section 6.4.1. and the reasons for premature discontinuation of study and / or study treatment. If the proportion of patients who withdraw across the dose groups is not fairly balanced, the impact on the primary variables will be further explored. To further explore the missingness pattern with regards to the “missing at random” assumption, the mean of the baseline values of the efficacy variable will be summarized for patients with and without post-baseline observations, by treatment group and overall.

For the analysis of the primary and secondary variables, it cannot necessarily be assumed that data are missing at random. As the choice of primary analysis will be based on assumptions that cannot be verified, the robustness of the results of the primary analysis will be investigated through appropriate sensitivity analyses making different assumptions, in accordance with the EMA “Guideline on missing data in confirmatory clinical trials”. Detail missing data handling are specified in Section 6.2.1.4.

When appropriate, the following rules will be implemented so as not to exclude subjects from statistical analyses due to missing or incomplete data:

- **Date of CHF diagnosis**
For cases where start month and year are reported but day is missing, impute it with the 1st day of month. If the month is not available, this date will not be imputed.
- **Clinical outcomes**
For cases where start month and year are reported but day is missing, impute the maximum of (date of randomization, first date of study medication, 15.month.year).
For cases where only start year is reported or completely missing, impute the maximum of (date of randomization, first date of study medication, 15.01.year), but not later than death date if the subject died.
- **Heart failure related concomitant medication start date**
For case where start month and year are reported but day is missing, impute it with 15th day of month. For cases where only start year is reported or completely missing, impute it as maximum of (15.01.year, randomization).
- **Heart failure related concomitant medication stop date**

For case where stop month and year are reported but day is missing, impute it as minimum of [(15, month, year) and (last visit date) and (death date)].

If the stop day and month are missing, then the stop date will be imputed as minimum of [(15.12.year) and (last visit date) and (death date)].

If the date is completely missing then the stop date will be imputed as minimum of [the last visit date and death date]. If the concomitant medication is “Ongoing at subject's last visit”, for the respective stop date variable the ‘last visit date’ from the corresponding domain is merged in the concomitant medication database by data management programming.

- **Study medication start date for subjects took study medication**

If the start date and time is missing it will be imputed with the randomization date and time. If start date and time is recorded as earlier than randomization and cannot be clarified, date and time of randomization will be used for the statistical analysis.

- **Study medication stop date for subjects took study medication**

If the stop day is missing, but the stop month and stop year are available then the stop date will be imputed as minimum of [(15, month, year) and (last on treatment visit date before the observational visit) and (death date)].

If the stop day and month are missing or the date is completely missing then the stop date will be imputed as minimum of [the last on treatment visit date before the observational visit and death date].

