10.3.2.1 Subgroups

In order to assess the homogeneity of the dose response across the most important prognostic and predictive factors, subgroup analyses will be performed.

'Key' subgroups comprise:

- LVEF(%) at baseline: ≤ 25 vs. > 25
- NT-proBNP (pg/ml) at baseline: \leq median vs. $>$ median
- NYHA class at baseline: II vs. III / IV
- Prior β -blocker: yes vs. no

Truly exploratory analyses, i.e., mainly summary statistics, will be provided for a spectrum of demographic, disease and clinical characteristics, including

- Age (years): < 65 , $65-75$, > 75
- Gender: male vs. female
- Race: White vs. non-white
- Region: North America / South America / West Europe / East Europe / Asia
- Region: Japan vs. rest-of-the-world (analysis to be included in reports specific for Japan only)
- BMI at baseline (kg/m^2): ≤ 30 vs. > 30
- Time of CHF diagnosis to randomization (months): ≤ 3 vs. > 3
- Prior hospitalization for heart failure: yes vs. no
- Etiology of CHF: ischemic vs. non-ischemic
- Diabetes: yes vs. no
- Atrial fibrillation: yes vs. no
- Hypertension: yes vs. no
- Prior CHF medication:
 - Prior β -blocker in max tolerated dose: yes vs. no
 - Prior use of ivabradine: yes vs. no
 - Prior use of aldosterone antagonist: yes vs. no
 - Prior use of ACE inhibitor: yes vs. no
 - Prior use of ARB: yes vs. no
 - Prior use of angiotensin receptor-neprilysin inhibitor (ARNI): yes vs. no
- Estimated GFR ($\text{ml}/\text{min}/1.73 \text{ m}^2$): ≤ 60 vs. > 60

Further details will be described in detail in the SAP.

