4.5.4 Subgroup analyses

In order to assess the homogeneity of the dose response across the most important prognostic and predictive factors, subgroup analyses will be performed.

‘Key’ subgroups include:

- LVEF(%) at baseline: ≤ 25 vs. > 25
- LVEF(%) at baseline: ≤ 40 vs. > 40
- LVEF(%) at baseline: ≤ 45 vs. > 45
- NT-proBNP (pg/ml) at baseline: \leq median vs. $>$ median
- NYHA class at baseline: II vs. III / IV
- Prior β -blocker: yes vs. no

All other exploratory subgroups comprise demographic and baseline characteristics specified in section 6.1.2.

If the total number of subjects in a subgroup category is too small, the respective subgroup category will be either omitted from the analysis or combined with other categories, if a logical combination to another subgroup category is possible.

Prior hospitalization for heart failure is defined based on one of inclusion criterions.

CRF item (subject group) selected	Prior hospitalization (outpatients visit)
CHF Hospitalization/ unscheduled outpatient clinic visit with BNP/NTproBNP measurement in the last 3 months	Yes
Only BNP/NTproBNP measurement in the last 4 weeks	No
Combination of CHF Hospitalization/ unscheduled outpatient clinic visit with BNP/NTproBNP measurement in the last 3 months and additional measurement in the last 4 weeks	Yes

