6.1.2 Demographic and Baseline Characteristics

Descriptive summaries of demographics and baseline characteristics will be presented by treatment group and overall for the PPS LVEF, PPS BNP, FAS and SAF populations. Comparability of the treatment groups with respect to demographics and baseline characteristics will be assessed using the descriptive summaries. Same analyses will also be performed for subjects who prematurely discontinue study participation or intake of study medication.

The following demographic data will be summarized:

- Age at baseline (years);
- Age category: <65, 65-75, >75 years;
- Gender (male vs. female)
- Race and ethnicity;
- Height (cm);
- Weight (kg) at baseline;
- BMI (kg/m²);
- BMI category: ≤30 vs. >30 kg/m²;
- Tobacco smoking history
- Alcohol consumption history
- Recent caffeine-containing beverage and chocolate consumption history

The following baseline characteristics will be summarized:

- LVEF(%) at baseline: ≤ 25 vs. > 25
- LVEF(%) at baseline: ≤ 40 vs. > 40
- LVEF(%) at baseline: ≤ 45 vs. > 45
- LVEF(%) at baseline: \leq mean vs. $>$ mean
- NT-proBNP (pg/ml) at baseline: \leq median vs. $>$ median
- NYHA class at baseline: II vs. III / IV
- Prior β -blocker: yes vs. no
- Region: North America / West Europe / East Europe / Asia
- Region: Japan vs. rest-of-the-world (analysis to be included in reports specific for Japan only)
- Time of CHF diagnosis to randomization (months): ≤ 3 vs. > 3
- Prior hospitalization for heart failure: yes vs. no
- Etiology of CHF: ischemic vs. non-ischemic
- Diabetes: yes vs. no
- Atrial fibrillation: yes vs. no
- Hypertension: yes vs. no
- Prior CHF medication:
 - Prior β -blocker in max tolerated dose: yes vs. no
 - Prior use of ivabradine: yes vs. no
 - Prior use of MRA: yes vs. no
 - Prior use of ACE inhibitor: yes vs. no
 - Prior use of ARB: yes vs. no
 - Prior use of angiotensin receptor-neprilysin inhibitor (ARNI): yes vs. no
- Estimated GFR (ml/min/1.73 m²): ≤ 60 vs. > 60

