6.4.2 Subgroup analysis of efficacy variables

Primary, secondary and sensitivity analyses (without imputed values) of primary efficacy variables will be performed based on key subgroups. Additionally primary efficacy variables will be descriptively summarized based on exploratory subgroups.

Secondary efficacy variables will be descriptively summarized based on key subgroups and exploratory efficacy variables will be descriptively summarized based on LVEF(%) at baseline: ≤ 40 vs. > 40 .

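### SAP 4.3 leaves a heart-failure diagnosis date missing when the month is unknown, even where the recorded year alone settles the 3-month class used for baseline and exploratory subgroup summaries

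*SAP*

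**What the plan says.** SAP 4.3 opens its list of date rules by saying that, when appropriate, "the following rules will be implemented so as not to exclude subjects from statistical analyses due to missing or incomplete data". The first rule concerns the date of CHF diagnosis. If only the day is missing: "For cases where start month and year are reported but day is missing, impute it with the 1st day of month". If the month is missing: "If the month is not available, this date will not be imputed". A recorded year makes no difference.

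The variable that needs this date is in SAP 6.1.2: "Time of CHF diagnosis to randomization (months): ≤ 3 vs. > 3". The protocol lists it in section 10.3.2.1, not among the key subgroups but in the group introduced by "Truly exploratory analyses, i.e., mainly summary statistics, will be provided for a spectrum of demographic, disease and clinical characteristics". SAP 4.5.4 gives it the same status: "All other exploratory subgroups comprise demographic and baseline characteristics specified in section 6.1.2". Its efficacy use is in SAP 6.4.2: "Additionally primary efficacy variables will be descriptively summarized based on exploratory subgroups". SAP 6.4.3 adds summaries of adverse events and ECG abnormalities by exploratory subgroup.

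Neither document lets the class be set from the year alone.

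**The concern.** The analysis does not need a diagnosis date as such. It needs to know on which side of 3 months the patient falls. For a patient whose record shows a diagnosis several years ago and no month, the answer is certain, yet the rule discards it. Under a section meant to keep subjects with incomplete data in the analysis, they lose a class that their own data determine.

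The same rule set accepts some misclassification elsewhere. Setting a missing day to the 1st can move a patient across the cut. A true diagnosis on 31 January with randomization on 15 April is 74 days; the imputed 1 January makes it 104 days.

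At stake are one row of the baseline table and the descriptive efficacy, adverse-event and ECG summaries for this exploratory subgroup. If year-only dates are commoner for old diagnoses, which is plausible but not documented, the loss falls mainly on the class above 3 months.

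**Working it through.** The plan gives no figure on this point to reproduce, so the check is of calendar logic.

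**Inputs from the documents.** The no-month rule (SAP 4.3), the cut at 3 months (SAP 6.1.2), and an anticipated recruitment period of 13 months (SAP 3), so that randomization can fall in any calendar month.

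**Assumptions.** 3 months is taken as 91 days and a year as 365 days. The documents do not give the distribution of disease duration, the share of year-only dates or the share diagnosed within 3 months.

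**Step 1: when does the year decide the class?** Let R be the randomization date and Y the recorded year. The latest possible diagnosis is L = the earlier of 31 December Y and R; the earliest is E = 1 January Y. The class is certainly above 3 months if R − L > 91 days, and certainly 3 months or less if R − E ≤ 91 days.

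- *Y two or more calendar years before the randomization year.* R − L is at least 365 + 1 = 366 days, so the class is above 3 months on 100% of randomization days.
- *Y the previous calendar year.* On the n-th day of the year, R − L = n days. It exceeds 91 from day 92 on: 365 − 91 = 274 days, and 274/365 = 75%. Randomization in roughly January to March leaves the class open.
- *Y the randomization year.* L = R, so the year never proves more than 3 months. On the n-th day R − E = n − 1, which is at most 91 for n ≤ 92. The class is then certainly 3 months or less on 92/365 = 25% of days.

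**Step 2: how often would that be in practice?** This depends on disease duration. Taking exponential durations and randomization uniform over the calendar year (400,000 simulated patients per row):

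| Assumed median duration (years) | Year proves > 3 months, all patients | Same, among those truly > 3 months |
|---|---|---|
| 0.5 | 38% | 54% |
| 1 | 61% | 72% |
| 2 | 77% | 84% |
| 4 | 88% | 92% |
| 6 | 92% | 94% |
| 8 | 94% | 96% |

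These percentages say how decisive a recorded year would be. They do not say how many patients have only a year.

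**Step 3: possible effect on the reported share of recent diagnoses.** Let p be the true share within 3 months, all with a known month, and m the year-only rate among the rest. If percentages use only patients with a value, the reported share is p / [p + (1 − p)(1 − m)].

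- p = 5%: m = 5% gives 0.05/0.9525 = 5.2%; m = 20% gives 0.05/0.81 = 6.2%; m = 40% gives 0.05/0.62 = 8.1%.
- p = 10%: m = 5% gives 0.10/0.955 = 10.5%; m = 20% gives 0.10/0.82 = 12.2%; m = 40% gives 0.10/0.64 = 15.6%.

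If percentages use all patients in the analysis set, with missing shown separately, the share stays at 5% or 10% whatever m is. Both p and m are assumed.

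**The case against.** Declining to invent a month is a defensible, prespecified choice, and year-only imputation of outcome and medication dates in the same section serves other purposes. The variable is exploratory and descriptive. It is not a key subgroup and is not among the covariates of the adjusted analysis in SAP 6.2.1.5. Diagnosis precedes randomization, so missing dates are balanced across arms in expectation. The contrast is thin in any case: with 5–10% recent diagnoses, 384 patients give about 19–38 across six arms, and SAP 4.5.4 already allows a category that is too small to be omitted or combined. The year-only rate may also be low, since protocol 11.1 describes data checks and queries for completeness. All of this limits the importance of the point, and it stands. It does not justify discarding a class that is certain, because deriving the class requires no invented month.

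A reader might infer more than the documents support:

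- *That a recorded year nearly always shows more than 3 months.* It does not for same-year diagnoses, nor for previous-year diagnoses with randomization in about January to March. With short assumed durations it proves the class for only 54–72% of those truly above 3 months.
- *That these patients drop out of the baseline table.* They lack one value and remain in every other row. Partial dates still appear in the listings, and SAP 4.1 reports missing counts for metric data, though it does not say so for categorical tables.
- *That the recent share is overstated, or that a stated fraction of the longer-duration group is lost.* The first needs a non-missing denominator, which the SAP does not specify; the second merely repeats an assumed m.

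**Conclusion.** The point holds as a minor, costless improvement. The no-month rule withholds a class that is certain for every year-only diagnosis two or more calendar years before randomization, and for previous-year diagnoses on about 75% of randomization days. That runs against the purpose SAP 4.3 states for its rules. The effect is confined to one baseline characteristic and its exploratory descriptive summaries.

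The number of patients affected is unknown and could be close to zero. That the loss falls mainly on the class above 3 months rests on the assumption that old diagnoses are more often recorded by year only. Overstatement of the recent share needs, in addition, percentages based on non-missing patients. Nothing here touches the primary analysis, the key subgroups or the type I error, and no bias between dose groups follows from it.

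**What to change.** Keep the date un-imputed when the month is missing, and add to SAP 4.3 a derivation of the class alone:

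- more than 3 months, if 31 December of the recorded year is more than 3 months before randomization;
- 3 months or less, if 1 January of the recorded year is no more than 3 months before randomization;
- otherwise unknown.

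Show the unknown count by arm in the baseline table, and state whether percentages use all patients or only those with a value. State the length of 3 months in days so that the cut is reproducible.

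The cost is a few lines of SAP text and a short derivation in the program. No new data are needed, no date is invented, and no patient whose recorded year is right can be misclassified by it.
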